### **7.3.2 Post-Study SAEs**

Investigators are not obligated to actively seek SAE information in former study participants, but investigators are encouraged to notify Salix of any SAEs occurring at any time after a subject has discontinued or terminated study participation that they judge may reasonably be related to study treatment or study participation.

## **7.4 Documenting AEs and SAEs**

All AEs that occur after the subject has signed the ICF and during the course of the study, regardless of causality or seriousness, will be assessed and recorded in the subject's medical records and in the CRF. In addition, SAEs must be documented on the paper SAE Report Form.

A separate paper SAE Report Form should be used for each SAE. However, if at the time of initial reporting, multiple SAEs are present that are temporally and/or clinically related, they may be reported on the same SAE Report Form.

The investigator should attempt to establish a diagnosis for the event based on signs, symptoms, and/or other clinical information. In such cases, the diagnosis should be documented as the AE and SAE and not the individual signs/symptoms.

For clinically significant abnormal laboratory findings or other abnormal assessments meeting the definition of an AE or SAE, a diagnosis, if known (or clinical signs and symptoms if diagnosis is unknown), should be recorded by the investigator. If a diagnosis is unknown and clinical signs and symptoms are not present, then the abnormal finding should be recorded. When documenting as an SAE on the SAE Report Form, relevant laboratory data should either be recorded in the 'Details of Relevant Assessments' section of the SAE Report Form (including the reference range and units) or copies of the laboratory report (with reference ranges and units) should be sent with the SAE Report Form.

The SAE Report Form should be completed as thoroughly as possible and signed by the investigator or his/her designee before transmittal to Salix Product Safety or Designee. It is **very important** that the investigator provide his/her assessment of causality to study product at the time of initial SAE reporting.

Confidential

---

### **7.5 Follow-up of AEs and SAEs**

All AEs, regardless of seriousness, must be followed until resolution, until the condition stabilizes, until the event is otherwise explained, or the subject is lost to follow-up. The investigator is responsible to ensure that follow-up includes any supplemental investigations as may be indicated to elucidate as completely as practical the nature and/or causality of the AE. This may include additional laboratory tests or investigations, histopathological examinations, relevant hospital records (i.e. discharge summary), or consultation with other health care professionals.

Salix may request that the investigator perform or arrange for the conduct of supplemental measurements and/or evaluations. If a subject dies during participation in the study or during a recognized follow-up period, Salix should be provided with a copy of any postmortem findings, including histopathology.

For SAEs, new or updated information should be recorded on the originally completed paper SAE Report Form and all changes signed and dated by the Investigator or designee. By signing the SAE Report Form, the investigator or designee attests to the accuracy and completeness of the data and that he/she has reviewed and approved the report being submitted. The investigational sites IRB/IEC must be notified about SAEs in accordance with the requirements of the governing IRB/IEC.

### **7.6 Prompt Reporting of SAEs to Salix Pharmaceuticals**

SAEs must be reported promptly to Salix Product Safety or Designee once the investigator determines that the event meets the protocol definition of a SAE.

Prompt reporting of a SAE requires:

- Completion and transmission of the SAE Report Form to Salix Product Safety or Designee via fax within 24 hours of the investigator's knowledge of the event. In parallel, a corresponding AE with the SAE details should be entered into the AE CRF.
- Prompt reporting of additional information for previously reported SAEs should follow the same reporting timeframe as initial reports. In addition, the corresponding AE in the AE CRF (as applicable) should be updated to ensure all data points documented in the AE CRF are aligned with the matching data points on the paper SAE Report Form.

### **7.7 Pregnancy Reporting**

Pregnancies detected in subjects assigned to study treatment should be promptly reported to Salix Product Safety or Designee via fax as soon as the investigator is notified using the Salix Pregnancy Notification Form. If a female subject becomes pregnant following assignment to study treatment, the study product will be immediately discontinued and the subject will be

**Confidential**

---

followed until the outcome of the pregnancy is known. (Refer to the 'Females of Reproductive Potential' Section 4.4).

Salix Product Safety or Designee should be notified via fax of any updates on the status of the pregnancy as soon as the information becomes available by update and/or amendment of the initial pregnancy notification form.

Although pregnancy occurring in a clinical study is not considered to be an AE or SAE, any pregnancy complication or elective termination of a pregnancy, for medical reasons, will be recorded as an AE or SAE and followed as such.

#### **7.8      Transmission of SAE Report Forms and Pregnancy Notification Forms**

Completed SAE Report Forms and completed Pregnancy Notification Forms should be transmitted via the country specific fax numbers listed in the SAE Form Completion Guidelines which are provided in the Study Reference Manual.

For questions regarding SAE and/or Pregnancy reports, country specific phone numbers are listed in the SAE Form Completion Guidelines which are provided in the Study Reference Manual.

#### **7.9      Regulatory Reporting Requirements for SAEs**

The investigator, or responsible person per local requirements, must comply with the applicable local regulatory requirements related to the reporting of SAEs and expedited safety reports to regulatory authorities and their IRB/IEC.

## 8.0 STATISTICAL CONSIDERATIONS

A detailed statistical analysis plan will be prepared for this study. The plan will contain a discussion of the statistical methods, a description of the computational algorithms and data handling conventions, and specifications for the data summaries and listings. It will be finalized before database lock.

### 8.1 Randomization

Subjects who successfully complete the Screening Period will enter the Treatment Period and will be randomized in a 1:1 allocation to one of two treatment groups for the duration of the study as assigned by the means of centralized electronic randomization system.

Randomization will be stratified by study center within a country. Treatment groups are as follows:

- Treatment A: Rifaximin DR 800 mg BID
- Treatment B: Placebo BID

### 8.2 Determination of Sample Size

The information below provides the background information for sample size determination for the induction of clinical remission with endoscopic response at 16 weeks followed by clinical and endoscopic remission at 52 weeks. For placebo, the expected rates are based on data from a Phase 2 study (RETIC 03/06) conducted in subjects with active moderate Crohn's disease. The rates for Rifaximin DR are based on the assumption that Rifaximin DR will provide a somewhat higher induction of remission rate.

Expected rates for induction of clinical remission with endoscopic response at Week 16 are 40% for placebo and 55% for Rifaximin DR.

Based on a significance level of 5% (alpha 0.05), a sample size of approximately 240 subjects per treatment group will have at least 90% power to test the hypothesis that Rifaximin DR is superior to placebo for each co-primary endpoint considered individually. Approximately 80% power is available to detect significant differences between Rifaximin DR and placebo for both co-primary endpoints.

For the Long Term Treatment Phase, a 15% treatment effect is expected for both clinical symptom and endoscopic remission at Week 52. Based on this assumption and testing at a significance level of 5% (alpha 0.05), a sample size of approximately 210 subjects per treatment group will have at least 90% power to test the key secondary efficacy hypothesis that Rifaximin DR is superior to placebo when each key co-secondary endpoint is considered individually. In addition, approximately 80% power is available to detect significant differences between Rifaximin DR and placebo for each of the key co-secondary endpoints.

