| SAMPLE SIZE: | 
The information below provides the background information for sample size determination for the induction of clinical remission with endoscopic response at 16 weeks followed by clinical and endoscopic remission at 52 weeks. For placebo, the expected rates are based on data from a Phase 2 study (RETIC 03/06) conducted in subjects with active moderate Crohn's disease. The rates for Rifaximin DR are based on the assumption that Rifaximin DR will provide a somewhat higher induction of remission rate.
 
Expected rates for induction of clinical remission with endoscopic response at Week 16 are 40% for placebo and 55% for Rifaximin DR.
 
Based on a significance level of 5% (alpha 0.05), a sample size of approximately 240 subjects per treatment group will have at least 90% power to test the hypothesis that Rifaximin DR is superior to placebo for each co-primary endpoint considered individually. Approximately 80% power is available to detect significant differences between Rifaximin DR and placebo for each of the co-primary endpoints.
 
For the long term treatment phase, a 15% treatment effect is expected for both clinical symptom and endoscopic remission at Week 52. Based on this assumption and testing at a significance level of 5% (alpha 0.05), a sample size of approximately 210 subjects per treatment group will have at least 90% power to test the key secondary efficacy hypothesis that Rifaximin DR is superior to placebo when each key co-secondary endpoint is considered individually. In addition, approximately 80% power is available to detect significant differences between Rifaximin DR and placebo for each of the key co-secondary endpoints.
 
An additional consideration for sample size determination is the application of an inflation factor of 20% to account for drop-out rates during the Induction and Long Term Treatment Phases of the study. This consideration suggested that 330 subjects per treatment group would be required at study entry.
 |
|---------------------|---|

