**Confidential**

---

An additional consideration for sample size determination is the application of an inflation factor of 20% to account for drop-out rates during the Induction and Long Term Treatment Phases of the study. This consideration suggested that 330 subjects per treatment group would be required at study entry.

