### **8.3 Analysis Populations**

#### **Intent-to-Treat (ITT) Population**

The ITT population will include all randomized subjects who take at least one dose of study drug.

**Per Protocol (PP) Population** will include all subjects in the ITT Population with the exception of those who failed to meet Inclusion Criteria 3 and 4; or met Exclusion Criteria 1, 2, 13 or 14.

The analyses of baseline characteristics and efficacy will be performed for the ITT Population. The primary efficacy analysis also will be performed on the PP Population as a sensitivity analysis. All safety analyses will be performed on the ITT Population.

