### **Long Term Treatment Phase**

There will be two key co-secondary endpoints of efficacy assessed during the Long Term Treatment Phase. The first is:

- Clinical symptom remission defined by (1) the total number of liquid/very soft stools for the 7 days prior to the Week 52 visit being  $\leq 10$  (from CDAI Item 1); AND (2) an abdominal pain rating of  $\leq 1$  (from CDAI Item 2) on each day for the 7 days prior to the Week 52 visit.

The second is:

- Endoscopic remission defined as a SES-CD score of  $\leq 2$  at Week 52. SES-CD scores will be calculated from centrally-read digital video of ileocolonoscopies performed at Week 52.

For each endpoint, the number and proportion of subjects with clinical and endoscopic remission will be summarized by treatment group for the ITT Population.

For each endpoint, the null hypothesis  $H_0: \pi_R - \pi_P = 0$  versus the alternative  $H_A: \pi_R - \pi_P \neq 0$  is of interest, where  $\pi_R$  is the binomial parameter for remission for the Rifaximin DR group, and  $\pi_P$  is the binomial parameter for remission for the placebo group. Subjects who require the initiation of rescue medication and/or surgery for CD will be considered treatment failures from the date of the introduction of the rescue medication and/or surgery, regardless of their actual response data. The Cochran-Mantel-Haenszel (CMH) test, stratified by country, will be used to test the hypothesis. Each null hypothesis of no difference will be rejected if the resulting p-value for the respective statistical test is less than 0.05. Significance for clinical

Confidential

---

and endoscopic remission will only be declared if both null hypotheses are rejected. As such, the overall Type I error rate will be maintained at the 5% level without adjustment for multiple comparisons.

If it is evident that the response variable is confounded with some of the background variables, then logistic regression will be performed using the background variables as covariates. The differences between this adjusted analysis and the previous unadjusted analysis will be noted, and the impact of such differences will be discussed.

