7.7.1.2 Long Term Treatment Phase

There will be two key co-secondary endpoints of efficacy assessed during the Long Term Treatment Phase. The first is:

- Clinical symptom remission defined by (1) the total number of liquid/very soft stools for the 7 days prior to the Week 52 visit being ≤ 10 (from CDAI Item 1); AND (2) an abdominal pain rating of ≤ 1 (from CDAI Item 2) on each day for the 7 days prior to the Week 52 visit.

The second is:

- Endoscopic remission defined as a SES-CD score of ≤ 2 at Week 52. SES-CD scores will be calculated from centrally-read digital video of ileocolonoscopies performed at Week 52.

For each endpoint, the number and proportion of subjects with clinical and endoscopic remission will be summarized by treatment group.

For each endpoint, the null hypothesis $H_0: \pi_R - \pi_P = 0$ versus the alternative $H_A: \pi_R - \pi_P \neq 0$ is of interest, where π_R is the binomial parameter for remission for the Rifaximin DR group, and π_P is the binomial parameter for remission for the placebo group. Subjects who require the initiation of rescue medication and/or surgery for CD will be considered treatment failures from the date of the introduction of the rescue medication and/or surgery, regardless of their actual response data. The Cochran-Mantel-Haenszel (CMH) test, stratified by country, will be used to test the hypothesis. Each null hypothesis of no difference will be rejected if the resulting p-value for the respective statistical test is less than 0.05. Significance for clinical and endoscopic remission will only be declared if both null hypotheses are rejected. As such, the overall Type I error rate will be maintained at the 5% level without adjustment for multiple comparisons.

If it is evident that the response variable is confounded with some of the background variables, then logistic regression will be performed using the background variables as covariates. The differences between this adjusted analysis and the previous unadjusted analysis will be noted, and the impact of such differences will be discussed.

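### Protocol 8.2 and the synopsis give each key co-secondary endpoint both 90% and 80% power, and the Week 52 figure is not the power of the planned ITT test

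*Protocol*

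**What the plan says.** Protocol 8.2 assumes a 15-point effect on each Week 52 endpoint at alpha 0.05 and states that "a sample size of approximately 210 subjects per treatment group will have at least 90% power to test the key secondary efficacy hypothesis" when each endpoint is taken individually. It then adds that "approximately 80% power is available to detect significant differences between Rifaximin DR and placebo for each of the key co-secondary endpoints". The synopsis carries the same pair of statements.

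For Week 16, 8.2 assumes 40% on placebo and 55% on active, and gives at least 90% individually with about 240 per arm. Its 80% sentence reads: "Approximately 80% power is available to detect significant differences between Rifaximin DR and placebo for both co-primary endpoints". The synopsis version reads: "Approximately 80% power is available to detect significant differences between Rifaximin DR and placebo for each of the co-primary endpoints".

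The 330 per arm at entry comes from "the application of an inflation factor of 20% to account for drop-out rates during the Induction and Long Term Treatment Phases of the study" (Protocol 8.2). The text does not say whether 20% is the total or applies to each phase. No Week 52 placebo rate is given.

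On the analysis, Protocol 8.3 says: "The ITT population will include all randomized subjects who take at least one dose of study drug". Protocol 8.7.2 and SAP 7.10.1 apply the Worst Case rule to the primary and key secondary endpoints: fewer than four diary days in the week, or a missing SES-CD, counts as non-response. The Week 52 claim needs both tests to succeed. SAP 7.7.1.2 states: "Significance for clinical and endoscopic remission will only be declared if both null hypotheses are rejected"; Protocol 8.6.1 has the same rule. SAP 7.3 refers to the protocol for the sample size justification and says that both studies will be terminated early.

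**The concern.** There are two problems. First, one endpoint at one sample size, effect and alpha cannot have both at least 90% and about 80% power. A literal reader cannot tell whether the chance of winning the Week 52 claim, which needs both endpoints, is about 80% or something lower.

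Second, powering on about 210 and inflating to 330 suits an analysis that loses its dropouts. This analysis keeps every dosed subject and scores missing outcomes as failures. That raises the number analysed and may shrink the observed difference, and the two effects work against each other. The figure on the page does not describe the test that will be run, and the inputs needed to compute the right one are not all stated.

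**Working it through.** **Inputs.** From Protocol 8.2: alpha 0.05; 40% vs 55% at Week 16; 15 points at Week 52; 240, 210 and 330 per arm; 20% inflation. The alternative is two-sided (8.6.1) and allocation is 1:1 (8.1). Week 52 placebo rates of 10% to 40% are assumptions.

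**Formula.** Pooled two-proportion z-test, an unstratified approximation to the country-stratified CMH test. With difference D and pbar the mean of the two rates:

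power = Phi{ [D - 1.96 sqrt(2 pbar(1 - pbar)/n)] / sqrt[(p0(1 - p0) + p1(1 - p1))/n] }

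Joint power is taken as the square of individual power (independent endpoints); positive correlation would raise it.

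**Week 16 reproduced.** n = 240, 0.40 vs 0.55: (0.15 - 1.96 x 0.0456)/0.0451 = 1.35, so power is 91.1%; joint 0.911 x 0.911 = 83%. This agrees with at least 90% individually and about 80% for both.

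**90% against 80%.** 0.90 x 0.90 = 0.81. The 80% is what two endpoints at 90% give jointly, and the Week 16 sentence in 8.2 describes it that way.

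**Where 330 comes from.** 210/0.8 = 263 and 240/0.8 = 300, neither of which is 330. 210/(0.8 x 0.8) = 328 does match. So 20% loss in each phase, 36% in all, is the natural reconstruction (330 to 264 to 211), but it is an inference and not stated text.

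**Week 52 at 210 per arm.** Individual power is at least 90% only if the placebo rate is about 27% or lower, or about 58% or higher. Without a stated rate, the figure can be neither confirmed nor refuted.

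**Week 52 as planned, 330 per arm, missing scored as failure.** If the 15 points applies to subjects with data and a fraction d is missing equally in both arms, both rates are multiplied by (1 - d). The difference becomes 12 points at d = 0.20 and 9.6 points at d = 0.36. Example, placebo 30%, d = 0.36: 0.192 vs 0.288, (0.096 - 1.96 x 0.03325)/0.03304 = 0.93, power 82.5%.

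Individual / joint power, %:

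| Placebo rate (assumed) | 210 per arm, none missing | 330, 15 points already counts missing as failure | 330, 20% missing in total | 330, 36% missing |
|---|---|---|---|---|
| 10% | 98.3 / 96.7 | 99.9 / 99.8 | 99.4 / 98.8 | 97.6 / 95.2 |
| 20% | 93.4 / 87.2 | 99.2 / 98.3 | 96.2 / 92.6 | 90.1 / 81.2 |
| 30% | 89.1 / 79.3 | 98.0 / 96.0 | 92.2 / 84.9 | 82.5 / 68.0 |
| 40% | 87.1 / 75.9 | 97.3 / 94.6 | 89.0 / 79.2 | 76.6 / 58.6 |

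At every rate shown, the planned analysis has more power than the 210-per-arm calculation with 20% missing, and less with 36% missing. If the 15 points already counts missing as failure, individual power is at least 97% at any placebo rate. With a correlation of 0.5 between the test statistics, joint power in the 36% column at 20%, 30% and 40% is 83%, 72% and 64%.

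**Week 16 as planned.** 330 per arm with 20% scored as failures: 0.40 x 0.8 = 0.32 and 0.55 x 0.8 = 0.44, giving 89.0% individually and 79% jointly. If 40% and 55% already count missing as failure, 330 per arm gives 97.3%.

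**The case against.** The strongest reply is that 8.2 makes a conditional statement about 210 subjects and does not call it the power of the 330-subject analysis. Powering on completers and inflating for drop-out is common practice, and several plausible scenarios meet the 90% floor. This stands so far as it goes: the 210-per-arm figure is not shown to be wrong. What is missing is the power of the test actually planned, and the assumptions needed to compute it.

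A reader might infer that the Week 52 endpoints are underpowered. The documents do not support that. The low figures need 36% missing, a placebo rate above about 20%, and a 15-point effect confined to subjects with data; none of these is stated. The protocol's 20% can equally be read as a total. Unequal drop-out could push power either way, but the documents give no basis for any particular imbalance.

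Nor is drop-out the same as missing data. Protocol 4.5 asks investigators to try to obtain the end-of-treatment assessments, including ileocolonoscopy, from subjects who withdraw. The missing-data sections do not say whether such an early assessment could serve at Week 52. The missing fractions above are therefore scenarios, not forecasts.

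It is also fair that *each* in the 80% sentences can be resolved from context and that no decision rule depends on it. The sentences are still wrong as written, and the synopsis disagrees with 8.2 on the co-primaries.

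**Conclusion.** The 80% sentences are wrong as written: Week 52 in 8.2, and both Week 16 and Week 52 in the synopsis. The figure fits joint power. Separately, the stated Week 52 power is not that of the planned ITT test, and the true figure may be higher or lower. On the scenarios above with placebo rates of 20% to 40%, it runs from 77% to 99% individually. That spread reflects the unstated placebo rate, the meaning of the 20%, and whether the 15 points counts missing as failure. Week 16 is little affected with 20% scored as failures (91% to 89%). All figures assume equal missingness and an unstratified test; the joint figures assume independence unless stated otherwise. Severity is minor: since both studies are to be terminated early, this corrects the planning statement and says nothing about achieved power.

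**What to change.** In Protocol 8.2 and the synopsis:

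(a) Change *each* to *both* for the 80% figures: Week 52 in 8.2, Week 16 and Week 52 in the synopsis.

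(b) Restate Week 16 and Week 52 power, individual and joint, for 330 per arm in the ITT population under the Worst Case rule. The sponsor should state the Week 52 placebo rate, whether 20% is the total or per phase, whether equal missingness is assumed, and whether the 15 points (and the 40% and 55% at Week 16) count missing as failure. Possible wording: *With 330 ITT subjects per arm, missing data scored as non-response, d% missing by Week 52, a placebo rate of x% and a 15-point difference [among subjects with data / counting missing as failure], power is a% for each key co-secondary endpoint and b% for both.*

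The cost is wording only, with no change to enrolment or analysis. The restated power may be higher or lower than the present figure. SAP 7.3 needs no edit, because it refers to the protocol.
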